### 4.2.2 Restrictions

#### 4.2.2.1 Restrictions regarding concomitant treatment

The following table provides an overview of permitted and restricted medication over the different study periods. The COPD maintenance therapy including long-acting anticholinergic, inhaled corticosteroids and long-acting  $\beta$ -adrenergic drugs given either alone or in combination should be discussed at Visit 1 in order to adapt optimal treatment management in tune with the [Table 4.2.2.1:1](#) (Permitted Medications and Medication Restrictions).

Patients receiving corticosteroids at baseline (inhaled corticosteroid component alone if taken as fixed combination with a bronchodilator) will continue treatment at the same dose or equivalent dose and regimen during their treatment period. If the patient withdraws from the treatment period, the dual ICS/LABA could be resumed.

[figure not shown]
Please refer to [Section 3.3.4.1](#) (Removal of individual patients).

ICS mono-product adjustment is allowed during COPD exacerbation and should be linked to the reported exacerbation event.

Proprietary confidential information.

© 2015 Boehringer Ingelheim International GmbH or one or more of its affiliated companies. All rights reserved.

This document may not - in full or in part - be passed on, reproduced, published or otherwise used without prior written permission.

**Proprietary confidential information.**

**© 2015 Boehringer Ingelheim International GmbH or one or more of its affiliated companies. All rights reserved.**

This document may not - in full or in part - be passed on, reproduced, published or otherwise used without prior written permission.

Table 4.2.2.1: 1 Permitted Medications and Medication Restrictions

Drug Class	Sub-class	Prior to study	Study Period		
			Screening Period	Treatment Period	Follow up Period
Corticosteroids	Inhaled corticosteroids (iCS) (stabilized 4wks prior to V1)	Permitted 	Permitted 	Permitted 	Permitted 
	Oral corticosteroids [≤10 mg prednisone per day or ≤20 mg prednisone every other day (or equivalent); stabilized 4 wks prior to V1]	Permitted	Permitted	Permitted	Permitted
	Injected corticosteroids local administration (e.g. bursitis)	Permitted	Permitted	Permitted	Permitted
	Nasal corticosteroid sprays	Permitted 	Permitted 	Permitted 	Permitted 
β-adrenergics	Inhaled short-acting β-adrenergics (SABA)	Permitted	Rescue medication (as supplied) only 	Rescue medication (as supplied) only 	Rescue medication (as supplied) only 
	Inhaled long-acting β-adrenergics (bid) (LABA) (e.g. formoterol / salmeterol)	Permitted	Permitted 	NOT permitted	Permitted
	Inhaled long-acting β-adrenergics (qd) (e.g. indacaterol, vilanterol)	Permitted	Permitted 	Study medication ONLY permitted	Permitted
	Oral and patch beta-adrenergics	NOT permitted	NOT permitted		Permitted
	Beta blockers (stabilized 6 wks prior to V1)	Permitted	Permitted	Permitted	Permitted
Anticholinergics	Short-acting anticholinergics (e.g. inhalation aerosol, nasal spray)	Permitted	Permitted 	NOT permitted	Permitted
	Long-acting anticholinergics (bid/qd) (e.g: commercial tiotropium, umeclidinium aclidinium, glycopyrronium)	Permitted	Permitted 	Study medication ONLY permitted	Permitted

Table 4.2.2.1: 1 Permitted Medications and Medication Restrictions (cont'd)

Drug Class	Sub-class	Prior to study	Study Period		
			Screening Period	Treatment Period	Follow up Period
Combinations	iCS/LABA (bid/qd) Switch to iCS mono-product at the same dose or equivalent dose and regimen during their treatment period. (e.g. fluticasone/vilanterol)	Permitted	Permitted 5+6	NOT permitted	Permitted
	iCS/SABA Switch to iCS mono-product at the same dose or equivalent dose and regimen during their treatment period.	Permitted	Permitted 5+6	NOT permitted	Permitted
	Inhaled long-acting anticholinergics/ LABA (e.g. glycopyrronium+indacaterol, umeclidinium+vilanterol)	Permitted	Permitted 5+6	NOT permitted	Permitted
	Short-acting anticholinergic/ SABA	Permitted	Permitted 	NOT permitted	Permitted
Antibiotics	For respiratory infections The use of antibiotics is not restricted and may be prescribed as medically necessary for COPD exacerbation episodes and / or infections.	NOT permitted	Permitted (except antibiotics for prevention of exacerbation of COPD)		
	Any other infections	NOT permitted	Permitted	Permitted	Permitted
Miscellaneous	Other investigational drugs (*see exclusion criterion #18 )	NOT permitted	NOT permitted		
	Cromolyn sodium / nedocromil sodium^3	Permitted	Permitted	Permitted	Permitted
	Antihistamines (including nasal route), antileukotrienes	Permitted	Permitted	Permitted	Permitted
	Methylxanthines	Permitted	Permitted	Permitted	Permitted
	Mucolytics not containing bronchodilators (stabilized 4 weeks prior to V1)	Permitted	Permitted	Permitted	Permitted
	Mucolytics containing bronchodilators	NOT permitted	NOT permitted		
	PDE-4 inhibitor (e.g. Roflumilast)	NOT permitted	NOT permitted		

1. Use rescue medication delivered at Visit 1 (or Visit 0 for patients involved in the sub-study)
2. Not permitted within 4 weeks prior to screening visit (w.o. 4 wks prior to V1)
3. Permitted if prescribed for non-asthma condition
4. Patients who were using roflumilast in the past may be included if their last use was a minimum of 3 months prior to Visit 1. In the event a patient with prior use of roflumilast is enrolled, past medical records are required to support and document why and when roflumilast was stopped.
5. Treatment(s) should be discontinued at the latest the day before Visit 2 without wash-out requirement.
6. Last dose of ICS/LABA combination product at the latest the day before Visit 2 and first dose of mono-ICS the day of Visit 2.

Proprietary confidential information.

© 2015 Boehringer Ingelheim International GmbH or one or more of its affiliated companies. All rights reserved.

This document may not - in full or in part - be passed on, reproduced, published or otherwise used without prior written permission.

#### 4.2.2.2 Restrictions on diet and life style

Not applicable to this trial.

### 4.3 TREATMENT COMPLIANCE

Each patient will be trained in the correct use of the Respimat® inhaler using the training Respimat® inhaler with inserted placebo cartridge. Please refer to [section 4.1.4.3](#).

Patients will be asked to return inhalation aerosols and devices (used and unused) to the study site. The trial medication adherence should be reviewed by the investigator and reported in the eCRF.

#### Estimating Compliance to trial medication

Knowing the time interval between clinic visits should provide the estimate of the number of puffs that should have been administered by the patient three or four Respimat® inhalers used during that period of time.

The Respimat® inhaler contains 60 actuations (30 daily doses). The dose indicator shows approximately how much medication is left. When the pointer enters the red area of the scale, there is, approximately, medication for 7 days (14 actuations) left.

The dose indicator scale is divided into 4 quarters. One-quarter used accounts for 7 days of treatment (14 actuations).

Once the dose indicator has reached the end of the red scale (i.e. all 30 daily doses have been used), the Respimat® inhaler is empty. Over a period of 3 months that is to say between 2 clinic visits, patient should return 3 Respimat® inhalers empty (the dose indicator has reached the end of the red scale). The acceptable medication compliance should have an overall value

**Proprietary confidential information.**

© 2015 Boehringer Ingelheim International GmbH or one or more of its affiliated companies. All rights reserved.

This document may not - in full or in part - be passed on, reproduced, published or otherwise used without prior written permission.

in the range from 80% to 100%. If the compliance is less than 80% the patient needs to be re-trained. Please refer to [section 4.1.4.3](#).

Randomised patients should not be discontinued for a lack of compliance without prior discussion with the local clinical monitor.

Figure 4.3:1 Respimat® inhaler dose indicator

## 5. VARIABLES AND THEIR ASSESSMENT

### 5.1 EFFICACY

In this study, it is important to note that lung function measurements are not used as criteria for treatment effectiveness. The primary efficacy endpoint is based on the annual rate of moderate/severe COPD exacerbations during a fixed-treatment period of 52 weeks.

#### 5.1.1 Endpoints of efficacy

##### Primary endpoint

[figure not shown]
- Annualised rate of moderate to severe COPD exacerbation during the treatment period (within 1 day\* after the last drug administration date).

##### Key secondary endpoint

- Time to first moderate to severe COPD exacerbation during the treatment period (within 1 day\* after the last drug administration date).

##### Secondary endpoints

- Annualised rate of exacerbation leading to hospitalisation during the treatment period (within 1 day\* after the last drug administration date).
- Time to first COPD exacerbations leading to hospitalisation during the treatment period (within 1 day\* after the last drug administration date).
- Time to all-cause mortality (within 1 day\* after the last drug administration date).

Proprietary confidential information.

© 2015 Boehringer Ingelheim International GmbH or one or more of its affiliated companies. All rights reserved.

This document may not - in full or in part - be passed on, reproduced, published or otherwise used without prior written permission.

## 5.1.2 Assessment of efficacy

### 5.1.2.1 Definition of moderate and severe COPD exacerbations

For the purpose of this study, a COPD exacerbation is defined as a complex of lower respiratory events / symptoms (increase or new onset) related to the underlying COPD, with duration of three days or more, requiring a prescription of antibiotics and / or systemic steroids and/or hospitalisation.

A complex of lower respiratory events / symptoms is defined as at least two of the following:

- Shortness of breath
- Sputum production (volume)
- Change in sputum colour
- Cough
- Wheezing
- Chest tightness

“Onset of exacerbation” will be defined by the onset of first recorded symptom. The “end of exacerbation” will be decided by the investigator based on clinical judgment.

Exacerbations will be classified as follows:

- Mild: a new prescription of maintenance bronchodilator only
- Moderate: patient receiving an exacerbation-related prescription of oral corticosteroids and/ or antibiotic not requiring hospitalisation.
- Severe: COPD-related hospitalisation including emergency room visit\*

To consider hospitalisation associated with COPD exacerbation, the information collected should include the start date of all COPD-related hospitalisations as well as the discharge date from the hospital or equivalent

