### 3.3.2 Inclusion criteria

1. All patients must sign an informed consent consistent with ICH-GCP guidelines prior to participation in the trial, which includes medication washout and restrictions.
2. Male or female patients, 40 years of age or older.
3. All patients must have a diagnosis of COPD [[P11-05865](#)] and must meet the following spirometric criteria: stable airway obstruction with a documented post-bronchodilator  $FEV_1 < 60\%$  of predicted normal (ECSC, [[R94-1408](#)]); and a post-bronchodilator  $FEV_1/FVC < 70\%$  at Visit 1 (See [Appendix 10.5](#) for ECSC predicted normal equations).

Historical spirometry data within the past 3 months either at the site or at a referral site may be used or PFT measurement may be taken at the investigational site (See [Appendix 10.5](#) spirometry documentation).

- 
4. Patients with a documented history (please refer to [section 8.3.1](#)) of at least one moderate to severe COPD exacerbation in the previous 12 months requiring treatment with systemic corticosteroids and/or antibiotics and/or related hospitalization.
  5. Investigator should also ascertain that the patient is symptomatically stable as defined by:
    - no evidence of COPD exacerbation requiring use of either antibiotics and/or steroids 4 weeks prior to visit 1,
    - no evidence of change in their usual COPD medication 4 weeks prior to visit 1.
  6. Patients must be current or ex-smokers with a smoking history of more than 10 pack years. (See [Appendix 10.5](#) calculation of number of pack years).
  7. Patients must be able to perform all trial related procedures at the investigator discretion including:
    - technically acceptable and eligible pulmonary function test (if performed at site)
    - vital status follow-up in case of discontinuation until the predicted exit date (i.e.: 52 weeks from first intake of randomised treatment + 21 days).

Proprietary confidential information.

© 2015 Boehringer Ingelheim International GmbH or one or more of its affiliated companies. All rights reserved.

This document may not - in full or in part - be passed on, reproduced, published or otherwise used without prior written permission.

- COPD exacerbation interview every 6 weeks in case of premature discontinuation until the predicted exit date (i.e.: 52 weeks from first intake of randomised treatment + 21 days).

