**Proprietary confidential information.**

© 2015 Boehringer Ingelheim International GmbH or one or more of its affiliated companies. All rights reserved.

This document may not - in full or in part - be passed on, reproduced, published or otherwise used without prior written permission.

\*Visit in emergency is defined as: an unscheduled emergency room visit resulting in prescription of oral corticosteroids and/ or antibiotic.

Only the investigator-diagnosed COPD exacerbation fitting the above criteria of moderate to severe COPD exacerbation will be used for the analysis of the annualized moderate to severe exacerbation rate as the primary endpoint.

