#### 5.1.2.2 Assessment of moderate and severe COPD exacerbations

Information regarding exacerbations will be collected by the physicians during the visits and will be recorded in the eCRF. During all telephone calls and clinic visits, the same questions regarding exacerbation will be addressed for collecting exacerbation-related details and then recorded in the eCRF.

At every clinical visit, the investigator will be asked to review (not to collect) the patient's reminder card and all telephone calls since the last clinical visit to ensure that all exacerbations have been recorded and that the exacerbations meet the definition of study exacerbation.

The investigator (or deputy) will record the COPD exacerbation information the length of time the patient is treated with the trial medication but also for patients who will discontinue early.

For all patients (completed/discontinued) the COPD exacerbation collection time of interest will be the planned 52-week + 21 days starting from visit 2.

If patients are hospitalised, the study site will be responsible for collecting and reviewing pertinent medical records so that an informed judgment can be made as to the primary cause for admission.

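### Does the oral-steroid wording in the Moderate class leave the primary endpoint's event count undefined?

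*Protocol*

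**What the plan says.** Protocol section 5.1.2.1 is headed "Definition of moderate and severe COPD exacerbations". It opens with a general definition: a complex of respiratory symptoms lasting at least three days and "requiring a prescription of antibiotics and / or systemic steroids and/or hospitalisation". A three-level severity list follows:

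- The lowest level is given as "Mild: a new prescription of maintenance bronchodilator only".
- The middle level, on which this point turns, is given as "Moderate: patient receiving an exacerbation-related prescription of oral corticosteroids and/ or antibiotic not requiring hospitalisation".
- The highest level, Severe, is an admission for COPD and takes in an emergency visit as well. The footnote describes that visit as "an unscheduled emergency room visit resulting in prescription of oral corticosteroids and/ or antibiotic".

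The counting rule for the primary endpoint closes the section: "Only the investigator-diagnosed COPD exacerbation fitting the above criteria of moderate to severe COPD exacerbation will be used". Time to first moderate to severe exacerbation, the key secondary endpoint, uses the same kind of event.

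The SAP does not restate the definition. Its sections 5.1 and 9.1 refer back to protocol sections 5.1.2 and 5.1.2.1. The rules shown in SAP 9.1 cover the 7-day collapse, the severity of collapsed events, fatal events shorter than three days, and admission to hospital. None of the visible text mentions steroid route.

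**The concern.** Oral is narrower than systemic. Take a patient who receives an injected or intravenous steroid as an outpatient or in an emergency room, with no oral steroid, no antibiotic and no admission. The event meets the opening definition. Taken literally, it is not Mild (more than a bronchodilator was given), not Moderate (no oral steroid or antibiotic) and not Severe (no admission, and the footnote again asks for an oral steroid or antibiotic).

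The counting rule refers to the criteria above it, which could mean the definition or the class list. One programmer or site could therefore count an event that another would leave out, in the primary and key secondary endpoints of a trial in more than 50 countries. At stake would be a primary event count that depends on the reader and, on the literal reading, some loss of power. The hospitalisation endpoints are not involved, because SAP 9.1 takes only events marked on the eCRF as admissions.

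**Working it through.** **1. The passages side by side**

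| Place | Treatment wording |
|---|---|
| Protocol 5.1.2.1, general definition | systemic |
| Protocol 3.3.2, inclusion criterion 4, for a moderate to severe event | systemic: "requiring treatment with systemic corticosteroids and/or antibiotics and/or related hospitalization" |
| Protocol 6.1, recovery from an exacerbation during screening | systemic |
| SAP 7.2, exacerbations in the previous year | steroids, no route given |
| Protocol 5.1.2.1, Moderate class | oral |
| Protocol 5.1.2.1, emergency-visit footnote | oral |

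The narrower word appears only in the two classification lines. The rules on which events qualify refer elsewhere. At each clinic visit the investigator is to "ensure that all exacerbations have been recorded and that the exacerbations meet the definition of study exacerbation" (protocol 5.1.2.2). Protocol 5.4 points to section 5.1.2 as a whole, and the fatal-event rule in SAP 9.1 tests events against the definition. The Mild class cannot satisfy the opening definition at all, so the list does not work as a strict gate. Under that section heading, an event meeting the definition is naturally moderate or severe.

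**2. Does moderate versus severe matter?** An emergency visit treated with a non-oral steroid could be placed in either class. The primary and key secondary endpoints combine the two, and the hospitalisation endpoints need a recorded admission. No endpoint shown depends on the placement.

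**3. Reproducing the plan's power**

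Inputs from protocol 7.6: rate 0.85 on tiotropium, ratio 0.88 (so 0.85 × 0.88 = 0.748), two-sided alpha 0.01, 3900 per arm, dispersion k from 0.625 to 0.9, and 15% loss of patient-years (t = 0.85).

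- V = (1/t)(1/r1 + 1/r2) + 2k
- Power = Φ( √n · |ln 0.88| / √V − 2.576 ), with |ln 0.88| = 0.1278
- At t = 1 and 90% power, the same variance gives 3426.7, 3563.3, 3745.4 and 3927.5 per arm, against 3427, 3563, 3745 and 3927 in Table 7.6:1.
- At t = 0.85 and k = 0.625: V = 2.513/0.85 + 1.25 = 4.207, giving 90.6%. At k = 0.9: V = 4.757, giving 86.1%. Both match the protocol.
- Key secondary: p1 = 0.65, p2 = 1 − 0.35^0.88 = 0.603. First events = 3900 × (0.65 + 0.603) = 4887. Power = Φ( √4887 × 0.1278/2 − 2.576 ) = 97.1%, against the stated 97%.

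**4. If the literal reading removed events**

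The documents give no share f for the affected events, so f is an assumption. Let it be equal in both arms, with the ratio and k unchanged, so that r1 becomes 0.85(1 − f). Planned events after the 15% loss are 3900 × (0.85 + 0.748) × 0.85 = 5297. First events are cut by the same share, which may overstate that loss, since a patient whose first event is uncounted can have a later counted one.

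| f (assumed) | Events uncounted | V (k = 0.625 / 0.9) | Primary power (k = 0.9 to 0.625) | First events | Key secondary power |
|---|---|---|---|---|---|
| 0 | 0 | 4.207 / 4.757 | 86.1–90.6% | 4887 | 97.1% |
| 2% | 106 | 4.267 / 4.817 | 85.6–90.1% | 4789 | 96.8% |
| 5% | 265 | 4.363 / 4.913 | 84.8–89.4% | 4642 | 96.2% |
| 10% | 530 | 4.535 / 5.085 | 83.3–88.0% | 4398 | 95.2% |

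The protocol applies its 15% loss to the primary endpoint only. Cutting first events by 15% as well (a further assumption) gives 93.9% at f = 0, then 93.3%, 92.5% and 90.9%.

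**The case for a change.** The best case for a change is that a counting rule for a primary endpoint should be written down rather than inferred. Wording that favours one reading is not a rule, and the closing sentence of 5.1.2.1 can fairly be read as requiring the Moderate or Severe class, where the word is oral. SAP 9.1 exists to settle edge cases of this definition and already does so for short fatal events. One more sentence before unblinding would cost almost nothing.

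The textual part of this stands: the two wordings differ, and nothing visible says which governs. Three things limit its weight.

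- Silence can be confirmed only for the public text. Content under the severity rules in SAP 9.1 is not shown.
- The eCRF is not in the documents. If its questions, which protocol 5.1.2.2 keeps the same at every contact, ask about systemic steroids, sites were aligned from the start. If it records only oral steroids, or if sites never entered such events, a late SAP sentence could not recover them.
- No distortion of the treatment comparison is shown. The wording is the same for both blinded arms.

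**Conclusion.** No change follows. This is a drafting inconsistency that analysts would most likely settle the same way, by counting events that meet the opening definition. Any doubtful case can be taken to the blinded report planning meeting the SAP already uses.

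The affected subset must meet four conditions at once: a non-oral systemic steroid, no oral steroid, no antibiotic and no admission. Its size is unknown. Under the literal reading, an assumed 2% share costs about 0.5 points of primary power and an assumed 10% share about 2.6 to 2.8 points (90.6 − 88.0 and 86.1 − 83.3). Key secondary power stays at or above 95.2% with full follow-up, or 90.9% if first events are also cut by 15%. These figures assume the same share in both arms, an unchanged ratio of 0.88 and unchanged dispersion. If the 0.85 planning rate itself came from oral-steroid and antibiotic events, which the documents do not say, nothing is lost against plan. Either reading, used consistently under the blind, gives a valid test and a valid rate ratio for the events it counts.

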**Proprietary confidential information.**

© 2015 Boehringer Ingelheim International GmbH or one or more of its affiliated companies. All rights reserved.

This document may not - in full or in part - be passed on, reproduced, published or otherwise used without prior written permission.

\*Visit in emergency is defined as: an unscheduled emergency room visit resulting in prescription of oral corticosteroids and/ or antibiotic.

Only the investigator-diagnosed COPD exacerbation fitting the above criteria of moderate to severe COPD exacerbation will be used for the analysis of the annualized moderate to severe exacerbation rate as the primary endpoint.

#### 5.1.2.2 Assessment of moderate and severe COPD exacerbations

Information regarding exacerbations will be collected by the physicians during the visits and will be recorded in the eCRF. During all telephone calls and clinic visits, the same questions regarding exacerbation will be addressed for collecting exacerbation-related details and then recorded in the eCRF.

At every clinical visit, the investigator will be asked to review (not to collect) the patient's reminder card and all telephone calls since the last clinical visit to ensure that all exacerbations have been recorded and that the exacerbations meet the definition of study exacerbation.

The investigator (or deputy) will record the COPD exacerbation information the length of time the patient is treated with the trial medication but also for patients who will discontinue early.

For all patients (completed/discontinued) the COPD exacerbation collection time of interest will be the planned 52-week + 21 days starting from visit 2.

If patients are hospitalised, the study site will be responsible for collecting and reviewing pertinent medical records so that an informed judgment can be made as to the primary cause for admission.

